### **Screening Evaluations:**

After informed consent has been obtained and documented, participants will be screened for study-specific inclusion/exclusion criteria through screening visit assessments and procedures, which will occur within a 2 week period, no more than 3 months prior to the apheresis procedure and randomization. A detailed schedule of study assessments is found in **Appendix B**.

Each participant enrolled in the trial will be assigned a unique study number that will be used in all study-related documentation pertaining to the individual. The number will be a combination of the site number provided by the coordinating centre and a sequential enrolment number. In the event of a screen failure, a 2nd screening visit may be performed; however, a new study number must be assigned to the participant.

Screening evaluations will include the following:

- Recording of patient demographics, medical history, concomitant medications
- Physical examination by the principal investigator or a sub-investigator
- Vital signs (blood pressure, heart rate, respirations) and measurement of height and body weight
- Assessment and recording of WHO functional class (see **Appendix C**)
- Chest x-ray
- Resting 12 lead ECG
- O2 saturation measurement by peripheral device
- Laboratory tests: sodium, potassium, chloride, TCO2, blood sugar, BUN, Creatinine, Calcium, Magnesium, phosphorus, alkaline phosphatase, total bilirubin, CPK, troponin, AST (SGOT), ALT (SGPT), LDH, gamma GT, albumin, uric acid, serum ferritin, CBC with differential, ESR, PT, PTT, INR, HIV-1/2, HBV, HCV, HTLV-I/II, *Treponema pallidum* (TP) Antibodies, β-hCG for females with childbearing potential
- Urine collection for routine and microscopic analysis
- 6-minute walk distance (6MWD) test and Borg dyspnea index (two 6MWD tests to be performed within 24 hours, not less than 1 hour apart, with ≤ 15% variation) (see **Appendix D and E**)

Consenting participants who meet all eligibility criteria will undergo an apheresis procedure which will be performed at the participating site according to the SAPPHIRE Apheresis protocol (**Appendix F**). Participants will then be randomized to one of three study groups (Figure 1) following a satisfactory cell collection procedure and receipt of the sample by the Cell Manufacturing Facility (CMF). In the case of an unsuccessful apheresis, the participant would be given the option of undergoing a second apheresis procedure which should be scheduled within the 3-month screening period to avoid having to repeat screening procedures.

## 4.2 Withdrawal/Follow-up

### Premature Participant Withdrawal

Premature withdrawal of study participants may be based on any of the following reasons:

- Sponsor Recommendations (i.e. Safety-specific protocol requirements)
- Investigator Decision (i.e. Participant non-compliance or if participant cannot safely perform the procedures required in the protocol)
- Participant Decision (No longer wishes to take part in the trial)
- Death of the study participant
- Pregnancy during the 12 month study treatment/follow-up period (refer to Section 9.7 for guidance)

Following the receipt of the study product, a participant may withdraw consent for study follow-up at any time for any reason. In addition, a participant may be considered withdrawn for failure to return for study visits or become lost to follow up for any other reason.

If a participant withdraws consent for further study follow-up procedures and assessments, every effort should be made to continue to follow the participant for their safety and the collection of safety data. This would ideally include completion of a treatment phase premature withdrawal visit (see Treatment Phase Premature Withdrawal Visit) and the long-term follow-up registry annual phone calls.

The PI or research staff must determine whether the participant wishes to:

- Withdraw from study follow-up procedures and assessments, but permit telephone follow-up or review of clinic/hospital records for data collection
- Withdraw from study follow-up procedures and assessments and decline further contact, however permit their accumulated data to be included in the study analysis
- Withdraw from study follow-up procedures and assessments and decline further contact and access to personal health information and indicate data collected to date cannot be used in the final analysis. Source documents cannot be destroyed until completion of the long-term storage period (25 years).

The primary reason for premature withdrawal and the participant's decision to decline study follow-up must be recorded in the participant's source documents and on the Treatment Phase Exit eCRF.

#### Lost to Follow-up

In the case of a participant becoming lost to follow up, the investigator should demonstrate "due diligence" by performing the following recommended steps:

- Contact participant three times and clearly document those efforts. Contacts may be done either by telephone contacts, email or mail correspondence. Documentation of any telephone contacts should also include dates and times
- If unsuccessful after three times, a registered letter should be sent to the participant's address requesting the participant to sign for the letter to attempt to confirm survival status
- If no response, clearly document efforts and complete all source documents and eCRFs as applicable
- Confirm status as lost to follow-up.

#### Treatment Phase Premature Withdrawal Visit

In the event of early withdrawal from the 12-month treatment phase of the trial, a Premature Withdrawal visit will be completed with the following timing:

1.  $30 \pm 2$  days after the last study product injection (for participants who exit the treatment phase between Months 0-4 or 6-10)
2.  $5 \pm 2$  days following withdrawal from the treatment phase (for participants who exit the treatment phase between Months 4-6 or 10-12)

The following assessments will be performed:

- Physical exam by the principal investigator or co-investigator
- Concomitant medication recording
- Vital signs (blood pressure, heart rate, respirations)
- Assessment and recording of WHO functional class (see Appendix C)
- O2 saturation (peripheral device)
- Laboratory tests: sodium, potassium, chloride, TCO2, blood sugar, BUN, creatinine, calcium, magnesium, phosphorus, alkaline phosphatase, total bilirubin, CPK, troponin, AST (SGOT), ALT (SGPT), LDH, gamma GT, albumin, uric acid, serum ferritin, CBC with differential, ESR, PT, PTT, INR, brain natriuretic peptide (BNP), C-reactive protein (CRP)
- Urine collection for routine and microscopic analysis
- Urine pregnancy test for females with childbearing potential
- 6MWD test and Borg dyspnea index (see Appendix D and E)
- Resting 12 lead ECG
- Assessment of adverse events and serious adverse events

### 4.3 Baseline Patient Characteristics

Baseline patient characteristics will include the following variables:

- Age
- Gender
- Race
- PAH Diagnosis (Idiopathic/Hereditary, Scleroderma, Drugs/Toxins, Congenital Heart Defects)
- WHO Functional Class (at Month 0)
- Oxygen use
- Type of PAH medication (s)
- Number of PAH medications
- Oxygen Saturation (at Month 0)
- 6MWD (at Month 0)
- RHC Results (at Month 0)
  - mPAP
  - PCWP
  - CO
  - PVR
- PFT results (at Month 0)
- Medical Conditions

## Section 5 – Analysis

### 5.1 Outcome Definition

Outline and explain all primary and secondary outcomes. Include the specification of outcomes as they relate to timing and list the order in which primary or key secondary end points will be tested.

#### Primary Outcome

The primary outcome of this trial is 6-minute walk distance (6MWD) at 6 months.

#### Secondary Outcomes

Secondary outcomes include 6-minute walk distance (6MWD) at 3, 9 and 12 months, pulmonary hemodynamics (i.e., PAP, cardiac output, RAP PAWP) at 3, 6, 9 and 12 months, Quality of Life measured by the SF-36 at 6 and 12 months, combined endpoint of death, or clinical worsening of pulmonary arterial hypertension at 6 and 12 months and measures of RV function by echocardiography at 6 and 12 months.

Clinical worsening of pulmonary arterial hypertension will be defined by any of the following:

1. All-cause mortality
2. Hospitalization due to worsening cardiopulmonary status attributable to progression of disease
3. Decrease in 6MWD by  $\geq 15\%$
4. Worsening of WHO functional class.

### 5.2 Analysis Methods

#### Descriptive Statistics

Descriptive statistics will be used to compare demographic characteristics and baseline prognostic factors of participants allocated to the three study arms. Measures of central tendency and dispersion will be calculated for all baseline variables in each study arm. Clinically important differences will be identified and adjusted for in all subsequent adjusted analyses. The normality of the distributions for primary and secondary outcome measures on a continuous scale will be assessed by visual inspection of histograms and normal probability plots. Normalizing transformations will be applied where necessary.

#### Analysis of Primary Outcome (6MWD at 6 months)

The primary analysis of our primary outcome, 6MWD assessed at baseline, one, two, three, four and six months, will use a general linear model with time (coded as a categorical variable) and group by time interaction as fixed covariates. As recommended for efficient analyses of longitudinal randomized controlled trials, baseline differences between the arms will be constrained through exclusion of the main effect for group. In addition to providing the unadjusted effect, we will adjust our estimate for the stratification factors (6MWD  $\leq 300$ m vs.  $> 300$ m and scleroderma APAH vs. all other eligible PAH categories), as well as age, gender and

baseline medication use (PDEVi and sGC stimulators vs. all other PAH-specific medications). The model will be estimated using Restricted Maximum Likelihood (REML), and degrees of freedom will be computed using the Kenward-Roger approach. Suitable covariance structures to account for correlation among repeated measures over time will be identified using likelihood ratio tests and information criteria (AIC and BIC). For the primary endpoint, the adjusted least square mean difference between the average of the two active treatment arms (Arms 2 and 3) versus placebo (Arm 1) at 6 months, together with 95% confidence interval, will be obtained and assessed at the two-sided 5% level of significance. Additional exploratory pairwise comparisons of least square mean differences at one, two, three, and four months will be conducted.

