Appendix D – 6 Minute Walk Distance (6MWD) Test Protocol

CONFIDENTIAL

The 6MWD test is designed to evaluate exercise capacity while performing an everyday activity. It is often used for measuring the response to medical interventions in patients with moderate to severe heart or lung disease and has the advantage of not requiring complicated exercise equipment or specialized technicians to administer the test.

The specific details that describe the technical aspects of the test, the required equipment, the safety aspects, the participant instructions, and the test procedure are found in the SAPPHIRE

6 Minute Walk Distance Test Protocol found in the Study File Binder.

General Considerations:

- 1. The 6MWD test is a non-encouraged test.
- 2. Repeat tests throughout the trial should be performed at about the same time of day in order to minimize intraday variability.
- 3. The location of the 6MWD test must be of adequate length and width and rarely traveled by other individuals. The same walking course location should be used for each participant at the study site.
- 4. Testing should be performed in a location where a rapid, appropriate response to an emergency is possible.
- 5. Participants who require supplemental oxygen should be tested using the same method of delivery (i.e. liquid oxygen or oxygen tank) and flow rate for all 6MWD tests performed throughout the trial. If the flow rate must be increased during subsequent visits due to worsening gas exchange, this should be noted on the worksheet.

The Screening 6MWD Test:

- 1. Two 6MWD tests will be performed within 24 hours with at least one hour of rest between them.
- 2. In order for a participant to be eligible for further study participation, there must be $\leq 15\%$ variation between the two tests, and the averaged result must be ≥ 125 meters and ≤ 440 meters.
- 3. The % difference between the tests will be calculated by taking the absolute value of the difference between the two distances and dividing it by the larger of the two walk distances.

Testing for Other Study Visits:

For all other study visits, a single 6MWD test will be performed. The Month 0 6MWD distance test will be used as the baseline value for subsequent comparisons during the study.

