## 2.2 Randomization and Blinding

### Randomization

Eligible participants will be randomized only following the completion of a satisfactory apheresis collection and receipt of the sample by the CMF. CMF personnel who have been trained by the sponsor to perform randomizations will access the SAPPHIRE web-based randomization system available from the Ottawa Methods Centre (OMC) located at OHRI. Personnel requiring access to this system will receive individual confidential login accounts from Data Management Services at the OMC.

After accessing the SAPPHIRE randomization system, the web-page will prompt the user to confirm participant eligibility by completing an electronic randomization case report form. Once completed, the web-based program will generate a randomization number on the screen. The requesting CMF user will print the screenshot containing the randomization number and will file it in the CMF participant binder. A copy will then be scanned and emailed to the study site for placement in the participant's study file.

Randomization to treatment allocation will be performed using a randomly permuted block design of fixed sizes of 3, stratified based on the average of the two screening 6MWD test results ( $\leq 300$  m vs.  $> 300$ m) and type of PAH (scleroderma associated PAH vs. all other eligible PAH types). Since our sample size for this late phase trial is relatively small, stratification is used to promote balance across the arms with respect to the baseline measure of the primary outcome, as well as type of PAH, an important prognostic factor for response to therapy. In particular, scleroderma associated PAH tends to progress more rapidly and show less favourable response to PAH-specific therapies. The allocation sequence will be generated using a computer-generated algorithm operated by the unblinded statistician for the trial located at the OMC. The study sponsor/CRO will monitor all randomizations throughout the conduct of the trial. The OMC will also generate a blinded email notification to the study site, study sponsor, and the CMF as confirmation of successful randomization. The CMF will subsequently receive a notification with the unblinded treatment allocation in order to proceed with manufacturing of the participant's study product.

Blinding

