## 2.3 Sample Size

A total sample size of 39 participants (13 per arm) in an analysis of covariance using a planned comparison between the average of the two treatment arms versus control achieves 80% power to detect a minimally important mean difference of **50 meters** in the primary outcome (6MWD) using an F-test with a two-sided 5% significance level. The SAS procedure GLMPOWER was used to conduct the calculation (SAS Institute Inc. 2008. SAS/STAT® 9.2. User’s Guide. Cary, NC: SAS Institute Inc). The common standard deviation is assumed to be 85 and the correlation between baseline and 6 months is 0.80. These estimates are similar to those observed in our PHACeT trial where the standard deviation was 80 meters and the correlation between baseline and 6 month was 0.86. To account for 10% potential attrition, we will enroll and randomize 45 subjects (15 allocated to each arm).

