#### Analysis of 6MWD at 12 months

To compare the effect of sustained delivery of 4 vs. 8 doses of the cell therapy product on 6MWD at 12 months (secondary objective 1), the regression model will include repeated measures up to 12 months and be used to estimate the adjusted least square mean difference between Arm 2 and Arm 3 at 12 months, together with 95% confidence interval. Additional pairwise comparisons of least square mean differences at 7, 8, 9 and 10 months will be conducted.

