## 5.6 Programming Plans

Data manipulations and statistical analyses will be performed using SAS version 9.4 (SAS Institute Inc., Cary, North Carolina, USA).

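### Leaving out the group main effect does not, under the usual SAS coding, equalise the arms at Month 0; the SAP should write the baseline constraint into the model itself

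*SAP*

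**What the plan says.** SAP 5.2 (Analysis of Primary Outcome) and Protocol 11.4 treat baseline as one of six outcome times, with months 1, 2, 3, 4 and 6. The fixed effects are "time (coded as a categorical variable) and group by time interaction as fixed covariates", and "baseline differences between the arms will be constrained through exclusion of the main effect for group", with a textbook cited for the approach. Estimation is by REML with Kenward-Roger degrees of freedom. The primary contrast is the mean of Arms 2 and 3 minus Arm 1 at Month 6.

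On covariates: "In addition to providing the unadjusted effect, we will adjust our estimate for the stratification factors", plus age, gender and baseline medication. The adjusted difference is the one tested at the 5% level.

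Protocol Appendix D identifies baseline: "The Month 0 6MWD distance test will be used as the baseline value for subsequent comparisons during the study". The walk-distance stratum is a different quantity, because randomization is "stratified based on the average of the two screening 6MWD test results", cut at 300 m.

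SAP 5.6 says that "statistical analyses will be performed using SAS version 9.4". Neither document names a procedure, a parameterisation or a reference visit, and neither gives code.

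The sample size (SAP 2.3) relies on baseline adjustment: "The common standard deviation is assumed to be 85 and the correlation between baseline and 6 months is 0.80".

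For Month 12, "the regression model will include repeated measures up to 12 months", and the continuous secondary outcomes follow a similar approach.

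**The concern.** The text gives an aim (no arm differences at Month 0) and a means (omit the group effect). The means delivers the aim only under some codings. With full-indicator columns for arm, visit and their product, the interaction already contains the group main effect, so deleting that effect changes nothing. Three separate Month 0 means are fitted, and the Month 0 walk no longer adjusts the Month 6 contrast.

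What is at stake is precision. The 80% power assumes an ANCOVA that uses the 0.80 correlation between baseline and Month 6. The program would still print a Month 6 difference with a confidence interval, so the loss is easy to miss unless someone looks at the Month 0 means.

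**Working it through.** **Inputs.** From SAP 2.3: SD 85 m, correlation 0.80, difference 50 m, two-sided 5%, 13 per arm (39), raised to 15 per arm (45) for attrition. From SAP 5.2: 3 arms, 6 visits.

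**1. The plan's own figure.** Residual SD = 85 × √(1 − 0.80²) = 51.0 m. Contrast SE = 51.0 × √(1/13 + 1/26) = 17.3 m. The noncentral t with 35 df gives 80.1% power, so the stated 80% is reproduced.

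**2. What the fixed effects allow.** With 3 arms and 6 visits there are 3 × 6 = 18 cell means. Constraining Month 0 leaves 6 visit means plus 2 × 5 post-baseline arm differences, which is 16.

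| Coding, group main effect left out | Rank | Free arm differences at Month 0 |
|---|---|---|
| Full-indicator (CLASS), any reference visit | 18 (also 18 with group) | 2 |
| Full-rank reference-cell, Month 0 as reference | 16 | 0 |
| Full-rank reference-cell, Month 6 as reference | 16 | 2 (the Month 6 differences are fixed at zero) |
| Effect coding | 16 | 2 |
| CLASS, group set to one common level at Month 0 | 16 | 0 |

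Two of the five rows deliver the stated aim. For the 12-month 6MWD model (11 visits) the CLASS rank is 3 × 11 = 33 with or without group, against 11 + 2 × 10 = 31 when constrained. Secondary outcomes have fewer visits, but the gap is again 2.

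**3. Loss with no other adjustment.** SE = 85 × √(1/13 + 1/26) = 28.9 m; with 36 df, power is 39.2%. The variance ratio is 1/(1 − 0.80²) = 2.78. Generalised least squares gives the same two SEs under compound symmetry and under an autoregressive structure.

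**4. Loss in the adjusted model.** The 300 m stratum recovers part of the information. Let a share p of participants be in the smaller stratum, and let r be the correlation of the screening mean with Month 6. If walk distance is normal, R² = r² φ(z_p)² / [p(1 − p)], with 35 df. The documents give neither p, nor r, nor the shape.

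| Assumption (13 per arm) | R² | Power |
|---|---|---|
| Normal, r 0.60, p 0.10 | 0.123 | 44% |
| Normal, r 0.80, p 0.20 | 0.314 | 53% |
| Normal, r 0.80, p 0.50 | 0.407 | 59% |
| Normal, r 0.86, p 0.50 | 0.471 | 64% |
| Uniform, r 0.80, p 0.50 | 0.80² × 0.75 = 0.480 | 65% |

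A more favourable pairing goes higher: uniform with r 0.86 and p 0.50 gives R² = 0.86² × 0.75 = 0.555, SE = 28.87 × √0.445 = 19.3 m, and 71%.

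Suppose PAH type, age, gender and medication together explain an assumed 10, 20 or 30% of the remaining variance (normal, r 0.80, 31 df). Power is then 63, 68 or 74% for a 50/50 split, and 57, 62 or 68% for 20/80. The constrained model with the same four df spent and no gain from those covariates keeps 79.8%.

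**5. With 45 completers.** Constrained 86%; unadjusted 44%; with the stratum 49–70% over the normal-shape range; with the other covariates (50/50, r 0.80) 70, 75 or 80%.

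**The case against.** The strongest reply is that the constraint is itself a requirement of the SAP. A program that leaves the Month 0 means free breaches that sentence, and a method reference is attached to it. This stands. A reader might infer that the SAP prescribes an unconstrained analysis, or that the trial has 39% power. The documents support neither: the intent is explicit, no SAS procedure is named, CLASS coding is an inference from the software and the REML/Kenward-Roger wording, and 39% belongs to the unadjusted estimate rather than the adjusted primary one.

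A reader might also infer bias. There is none: without the constraint, the Month 6 contrast is still an unbiased randomised comparison. Nor is the Month 6 reference row a realistic silent error, because it forces the primary effect itself to zero and would be noticed.

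The intermediate power figures do depend on an undocumented stratum split, correlation, distribution shape and covariate strength. Screening walks are also restricted to 125–440 m, so normality is doubtful.

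What remains is narrow but firm. The one instruction the text gives a programmer, to leave out the group effect, does not meet the text's own requirement in a common coding of the named software. That is algebra and needs no clinical assumption.

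**Conclusion.** The point holds as a specification gap with a conditional loss of precision. Under CLASS coding the stated mechanism constrains nothing (rank 18 against 16; 33 against 31 for the 12-month 6MWD model). At 13 per arm, power for 50 m would fall from 80% to 39% unadjusted. In the adjusted primary model it would be roughly 44–65% with the stratum, and about 74% if the remaining covariates explain an assumed 30% of what is left. The ranks, the 80% and the 39% need only the plan's inputs and complete data; the figures in between are illustrations and move with the assumptions shown. If the constraint is coded as intended, nothing is lost. This is a cheap improvement rather than a flaw in the design or the estimand.

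**What to change.** Before lock, state in SAP 5.2 that all arms share one Month 0 mean and that arm terms enter at post-baseline visits only. Specify the implementation: either hand-built indicators for arm by post-baseline visit, or a group variable set to one common level for every arm at Month 0. Naming Month 0 as the CLASS reference level is not enough, because the rank stays at 18. Have the program verify that the Month 0 least-squares means are equal across arms. Use the same parameterisation for the 12-month 6MWD model and the continuous secondary outcomes.

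Separately, SAP 5.2 (Descriptive Statistics) and Protocol 11.3 let observed imbalance add covariates and let distribution checks change the scale. Fix the adjusted primary model to the listed covariates (two strata, age, gender, baseline medication) in untransformed metres, and report imbalance-driven or transformed models as sensitivity analyses.

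The cost is SAP wording and a few lines of code. No data or participants are added, and no power is lost against the planned ANCOVA.

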**Figure 1: The SAPPHIRE 3-Arm trial design.**

**Rationale for the 3-arm trial design:** The SAPPHIRE trial is designed to maximize the generation of relevant results to inform further development or application of the cell therapy approach. The rationale for the main elements of the study is summarized below.

- **Course 1:** The first 6 months of the study has a standard design with 2:1 randomization to study product or placebo:
  - Arm 1: Participants will receive 4 monthly placebo injections.
  - Arms 2 and 3: Participants will receive 4 monthly injections of the cell therapy product.

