## 2.4 Framework

This will be a superiority trial, with primary aim to determine whether receiving a course of 4 monthly doses of eNOS-EPCs will improve the 6 minute walk distance (6MWD) at 6 months

compared to placebo. A minimally important mean difference of 50 meters was considered for this hypothesis.

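### The 6MWD contrast at Months 1 to 4 is not named; read as all pairs, it splits two identically treated cell arms and widens each cell-versus-placebo interval by about 15%

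*SAP*

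**What the plan says.** SAP 2.1 describes Course 1 as a 2:1 comparison: "Arms 2 and 3: Participants will receive 4 monthly injections of the cell therapy product", and Arm 1 receives placebo. The cell arms part only with the first Course 2 injection, at Month 6. Protocol 7.4 places the Month 6 walk test before that injection, and Protocol Appendix H makes product delivery the last procedure of a visit. All walk tests from Month 1 to Month 6 therefore precede any difference in treatment between Arms 2 and 3.

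For Month 6, SAP 5.2 (Analysis of Primary Outcome) uses this. The contrast is "the average of the two active treatment arms (Arms 2 and 3) versus" placebo. SAP 2.3 powers the same contrast.

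For Months 1 to 4, the next sentence of SAP 5.2 reads: "Additional exploratory pairwise comparisons of least square mean differences at one, two, three, and four months will be conducted". Protocol 11.4 has the same sentence. Neither document lists the pairs or says whether the pooled contrast is also reported at these visits.

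SAP 5.1 lists 6MWD at 3 months among the secondary outcomes, whereas SAP 5.2 calls the Month 3 comparison exploratory. SAP 3.1 makes no multiplicity adjustment for secondary outcomes.

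**The concern.** In a model with three groups, pairwise differences of least square means ordinarily are 1 vs 2, 1 vs 3 and 2 vs 3. An average of two arms against a third is not a pair, and the plan had just described that contrast in other words. On this reading, two things follow at Months 1 to 4.

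- The cell effect is estimated twice, each time from half of the treated participants. In a trial of 45 that loses precision, and the two estimates of the same quantity can disagree by chance, with no rule for which to report.
- One of the three pairs compares arms that have had the same treatment. A nominally significant difference there would be noise.

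These visits are of interest. Month 3 6MWD is a listed secondary outcome, and this sentence is the only text that gives it a between-arm comparison. Month 4 falls one month after the fourth dose, and Protocol 6.5 says the one-month dosing interval was chosen because the phase 1 walk gain was largest then.

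**Working it through.** **Inputs.**
- SAP 2.3: "A total sample size of 39 participants (13 per arm) in an analysis of covariance"; "using an F-test with a two-sided 5% significance level"; "The common standard deviation is assumed to be 85 and the correlation between baseline and 6 months is 0.80"; 45 randomized, 15 per arm.
- SAP 2.4: "A minimally important mean difference of 50 meters was considered".
- Assumption, not in the plan: the same SD and correlation hold at Months 1 to 4.

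**Residual SD.** 85 × √(1 − 0.80²) = 85 × 0.60 = 51 m.

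**Standard errors with n per arm.**
- Pooled, average of Arms 2 and 3 vs Arm 1: 51 × √(1/n + 1/(2n)) = 51 × √(1.5/n).
- One cell arm vs Arm 1: 51 × √(2/n).

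**The plan's own figure first.** SAP 2.3 says that the design "achieves 80% power to detect a minimally important mean difference of" 50 m. With n = 13, the pooled SE is 51 × √(1.5/13) = 17.32 m. The noncentrality is (50/17.32)², on 1 and 39 − 4 = 35 degrees of freedom. Power is 80.1%, which reproduces the stated 80%.

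**The two contrasts compared** (residual degrees of freedom 35 for n = 13 and 41 for n = 15):

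| | Pooled | One cell arm vs placebo |
|---|---|---|
| SE, n = 15 | 16.1 m | 18.6 m |
| 95% half-width, n = 15 | 32.6 m | 37.6 m |
| Power for 50 m, n = 15 | 85.7% | 74.6% |
| SE, n = 13 | 17.3 m | 20.0 m |
| 95% half-width, n = 13 | 35.2 m | 40.6 m |
| Power for 50 m, n = 13 | 80.1% | 68.1% |

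**The ratio.** √(2/n) ÷ √(1.5/n) = √(4/3) = 1.155. The residual SD and n cancel, so with equal arms the 15% does not depend on the SD, the correlation or the common arm size.

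**Check in the longitudinal model.** Generalized least squares for the constrained-baseline model with 13 per arm gives a ratio of 1.155 at every visit, under compound symmetry (0.80) and under an autoregressive pattern scaled to 0.80 between baseline and Month 6. The level does depend on the covariance. At Month 4 the SEs are 17.3 and 20.0 m under compound symmetry, and 14.65 and 16.91 m under the autoregressive pattern. With unequal numbers (assumed 12 to 15 per arm), the ratio runs from 1.13 to 1.20.

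**Number of comparisons.** All pairs at four visits: 3 × 4 = 12, of which 4 are Arm 2 vs Arm 3. Pooled: 4.

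**Chance findings between the cell arms.** If Arm 2 vs Arm 3 were tested at 5% at each of the four visits, the chance of at least one significant result would be 1 − 0.95⁴ = 18.5% if the tests were independent. With baseline-adjusted between-visit correlation of 0.44, which compound symmetry at 0.80 implies as (0.80 − 0.64)/(1 − 0.64), it is about 16%. At an assumed 0.8 it is about 11%.

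**The case against.** **The pairs are not named.** A reader might infer that the plan definitely splits the cell arms and tests Arm 2 against Arm 3 four times. The text does not say so. The sentence follows the pooled contrast directly and may mean that contrast repeated at earlier visits. SAP 5.2 has an almost identical sentence for Months 7 to 10, straight after an Arm 2 vs Arm 3 contrast, where it can be read as that contrast repeated. This objection stands: all pairs is the ordinary reading, not the only one, and the 15% and the count of 12 are conditional on it. The contrast is unspecified on either reading.

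**No decision depends on it.** The comparisons are labelled exploratory. SAP 5.2 sets a 5% test only for Month 6, and the trial was not sized for earlier visits. This stands too, and it limits the point to a refinement.

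**The information is not lost.** The fitted model is the same, and only the reported contrast changes. The pooled estimate is the mean of the two cell-versus-placebo differences, with variance (V12 + V13)/2 − V23/4, where Vij is the variance of the difference between Arms i and j. With 15 per arm this is 2/15 − 0.5/15 = 1.5/15 times the residual variance, exactly the pooled value. That is correct, but a reader should not have to rebuild the natural estimate from three others.

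**Month 4 is not singled out by the documents.** The phase 1 peak came from 7 patients dosed over three days, and SAP 5.1 lists Month 3, not Month 4. This is fair, and the point does not rest on Month 4.

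**An early Arm 2 vs Arm 3 comparison has a use** as a descriptive check on pooling. This is also fair, although the plan states no such purpose.

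**Conclusion.** The point holds as a specification gap with an almost free gain in precision. The plan names the pooled contrast at Month 6 only and leaves Months 1 to 4 to unnamed pairwise comparisons. If these are all pairs, each cell-versus-placebo interval is √(4/3), or about 15%, wider than the pooled one. With 15 per arm, power for 50 m falls from about 86% to about 75%. The ratio needs only roughly equal arms; the metre and power figures also need SD 85 m and correlation 0.80 to hold at the early visits.

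Three stronger readings are not supported:
- That the Month 6 result is weakened. Its contrast is named, pooled and powered as stated.
- That no difference between Arms 2 and 3 can appear before Month 6. No treatment difference is expected by design, but chance differences can occur.
- That the same gap affects SF-36 and echocardiography at Month 3. Both are measured then, but SAP 5.1 lists them as outcomes only at 6 and 12 months.

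**What to change.** Replace the sentence in SAP 5.2 and Protocol 11.4 with: *The same contrast as the primary (average of Arms 2 and 3 versus Arm 1) will be estimated at Months 1, 2, 3 and 4 with 95% CI.*

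Add that any Arm 2 versus Arm 3 comparison before Month 6 is descriptive only, as a check on pooling.

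State whether Month 3 6MWD is a secondary outcome, as in SAP 5.1, or exploratory, as in SAP 5.2, and align the two sections.

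The cost is a short edit to each document before unblinding. No new data, visits or models are needed, and four contrasts are reported where the all-pairs reading would give twelve.
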